### 7.2.3 Regression Specifications

For all outcomes except timing of GDMT increases and ROI outcomes, ordinary least squares (OLS) regressions will be run with heteroskedasticity-robust standard errors clustered at the clinician level (to account for clustering of patients within clinicians). We will also explore the effect of clustering standard errors at the clinic level.

We will run a survival analysis to assess timing of GDMT increases.

Cost and outcomes estimate for the cost-effectiveness model will be obtained using EHR data, claims data, and literature-based sources. These data will be used to develop a decision tree analytical model with a state transition Markov cohort simulation to compute incremental cost effectiveness ratios (ICER), cost-effectiveness acceptance curves will be generated for all cost-effectiveness measurements. The effects of uncertainties from the model parameters will be evaluated by deterministic and stochastic sensitivity analyses. Following the World Health Organization's guidelines, we will define the willingness-to-pay (WTP) threshold as 1 to 3 times the local gross domestic product per capita. Interventions with an ICER below the threshold will be considered cost-effective. We will also compare the total dollar amount spent on implementing this program against the cost savings, if any, attributable to the interventions (CDS-OS + CDS-MTDM) to calculate the corresponding ROI.

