### 5.2 Hypothesis

$H_0$ : The implementation of a multifaceted, interdisciplinary intervention will not improve GDMT for patients with HFrEF.

$H_{A1}$ : The implementation of a multifaceted, interdisciplinary intervention incorporating an order set will improve GDMT for patients with HFrEF more than usual care.

$H_{A2}$ : The implementation of a multifaceted, interdisciplinary intervention incorporating a pharmacist referral will improve GDMT for patients with HFrEF more than usual care.

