## 6. STUDY METHODS

### 6.1 Study Design

This is a cluster randomized study designed to evaluate the effectiveness of interventions aimed at improving GDMT in patients with HFrEF. Clinicians were stratified based on practice specialty, location, and pharmacist referral habits (see details below) and were permuted block randomized to achieve 45%/45%/10% proportional distribution across the following arms respectively: (1) usual care (**Control arm**); (2) multi-pronged CDS inclusive of a patient portal message about GDMT, an interruptive advisory upon chart entry advising clinicians of the need to optimize treatment, and a BPA that links to a GDMT order set

(**CDS-OS arm**); and (3) multi-pronged CDS as in #2 but replacing GDMT order set with referral to integrated clinical pharmacist co-management (**CDS-MTDM arm**). Secondarily, each of the 5 clinical practice sites of roughly equal HFrEF patient loads were assigned to receive either an early or delayed education rollout.

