## 6.2 Randomization details

Permuted blocked randomization was completed once at the beginning of the study.

Randomization was stratified as described below given concerns about imbalances in GDMT prescribing practices across clinics, certain roles, and current MTDM referral practices.

Clinicians were divided into HF specialists and non-HF specialists given differences in practicing patterns and propensity for increased GDMT prescribing patterns among specialists.

Within Non-HF specialists, randomization was stratified on the following variables:

- Role: electrophysiology, interventional, non-invasive
- MTDM referral history: none/0%, 1%-100%
- Primary practice location: Northeast (GCMC, GWV, Orwigsburg), Central (GMC, Shamokin, Lewisburg), and West (GLH, Gray's Woods)

Within HF specialists, randomization was stratified on MTDM referral history. They were NOT stratified on practice location because there was not hypothesized to be a significant difference in practice as a function of location in this group.

We also generated permuted block randomized sequences for allocating any new clinicians who enter the system during the study. The study team collected information about role and primary practice location for any new clinician joining the system monthly. However, all new clinicians were assigned to the 0% MTDM referral history stratum, because new clinicians do not have an MTDM referral history in the system. Based on the pre-randomized sequence generated, the clinician would be assigned to an interventional arm. In generating these sequences, we assumed turnover rates would be equal across strata.

One hundred and fifty-five clinicians (103 current and 52 hypothetical) were randomized into control (45%), CDS-OS (45%) and CDS-MTDM arms (10%).

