The target audience for this education program are Cardiology clinicians (physicians (MD, DO) and advanced practitioners (PA, CRNP)) at Geisinger. Three clinics were selected for early education (i.e. before additional CDS and pharmacist referral interventions) and two clinics were reserved for late education (timed to occur after sufficient time has elapsed to assess the impact of the early education on its own). The early education programs were delivered over one month to each clinic with in-person attendance being encouraged.

Topics delivered in the early education sessions included:

1. Sacubitril / Valsartan (ARNI) in CHF
2. SGLT2 inhibitors in CHF
  - a. SGLT2i in Cardiovascular Disease & HFrEF
  - b. SGLT2i in HFrEF with Diabetes: What the Cardiologist should know
3. Management of HFrEF and chronic kidney disease (CKD)
4. Geisinger Pharmacist role in HFrEF

The early education sessions were delivered live, at each clinic location separately on a given date (either in-person or virtually depending on clinic preference).

Participants were encouraged by the lead PI to attend the live sessions if they were being offered at their clinic location. Continuing medical education (CME) credits were provided to attendees where applicable and lunch was provided during the live sessions. Presentations lasted about 30 minutes with a question-and-answer session to follow. An RSVP request was asked of those attending. Those missing their sessions were invited to a virtual session being held to try to increase attendance rates. The virtual sessions were recorded. The same approach will be used for delayed education.

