## 7. STATISTICAL ANALYSIS PLAN

### 7.1 Power analysis

Data will be collected from 4,300 patients assigned to the clinicians in the study. With CDS-OS and CDS-MTDM (versus control), we expect to have 80% power to detect approximately 5 and 9 percentage-point increases, respectively, in prescribing GDMT within 30 days, at two-tailed  $p < .05$  with robust standard errors clustered at the clinician level. With education versus delayed education, we expect to have 80% power to detect an approximately 5.5 percentage-point increase in prescribing GDMT, with robust standard errors clustered at the clinician level. Power analyses were conducted using DeclareDesign.

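### The CDS-MTDM versus control test (H_A2) rests on about 10 to 16 CDS-MTDM clinicians, but the plan fixes neither a small-sample variance method nor one model from which to read it

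*Combined protocol and SAP*

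**What the plan says.** Section 5.2 states two alternative hypotheses. The second, H_A2, is that the "intervention incorporating a pharmacist referral will improve GDMT for patients with HFrEF more than usual care". Section 6.1 says clinicians were "permuted block randomized to achieve 45%/45%/10% proportional distribution" across control, CDS-OS and CDS-MTDM, and section 6.2 gives 155 randomized clinicians: 103 current and 52 hypothetical.

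For every outcome except timing of GDMT increases and ROI, section 7.2.3 uses OLS with "heteroskedasticity-robust standard errors clustered at the clinician level". Section 7.1 describes the power analysis in similarly generic terms and reports "80% power to detect approximately 5 and 9 percentage-point increases, respectively", for CDS-OS and CDS-MTDM against control. Section 7.2 sets two-tailed p < 0.05 throughout. Its fallback to other tests is tied to the distribution of the outcome. Section 7.2.3 also explores clinic-level clustering.

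Section 7.2.2 adds education arm and CDS x education interactions to the CDS regressions. It makes delayed education the baseline level, gives a third level (other) to clinicians who arrived too late for an education arm, and keeps the interaction terms only if they are significant. On education, section 6.1 says "each of the 5 clinical practice sites of roughly equal HFrEF patient loads were assigned to receive either an early or delayed education rollout", and section 6.7 (Focused Education) says "two clinics were reserved for late education" while three had early education.

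**The concern.** A clustered sandwich variance is trustworthy when many clusters inform each coefficient. For CDS-MTDM versus control, the 10% arm supplies most of the variance, so its clinician count governs the effective degrees of freedom, however many control clinicians there are. Common software defaults correct by the total number of clinicians and so do not see the imbalance. Two analysts could both follow section 7.2.3 and obtain materially different p-values and intervals for one of the trial's two stated hypotheses, and a reader could not tell which had been planned. The estimate within a given model would be the same.

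The retention rule is a second, separate problem. It lets a significance test, itself clustered on the same few clinicians, decide which model and possibly which estimand answers H_A2. Neither the section 7.2 fallback nor exploratory clinic-level clustering addresses a small arm.

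**Working it through.** **1. Clinician counts (section 6.2).** CDS-MTDM: 0.10 x 103 = 10.3; 0.10 x 155 = 15.5. Control: 0.45 x 103 = 46.4; 0.45 x 155 = 69.8. Realised counts may differ: there are 3 x 2 x 3 + 2 = 20 strata, and block sizes are not given. Under assumed 9:9:2 blocks and equal strata, the 95% range is 5-16 of 103 and 9-22 of 155.

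**2. The plan's own power figure.** If patients split as clinicians do, the arms have 0.45 x 4,300 = 1,935 and 0.10 x 4,300 = 430 patients. Baseline rate and ICC are not given, so 5 and 9 points cannot be reproduced uniquely, but plausible inputs come close:

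| Clinicians | Baseline | ICC | Detectable, CDS-OS / CDS-MTDM |
|---|---|---|---|
| 103 | 20% | 0.02 | 5.1 / 8.5 points |
| 103 | 40% | 0.01 | 5.3 / 8.8 points |
| 155 | 30% | 0.02 | 5.2 / 8.7 points |

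The normal-theory ratio of the two is sqrt[(1/0.45 + 1/0.10)/(2/0.45)] = 1.66, against 9/5 = 1.8 as stated. Rounding or an allowance for degrees of freedom could explain the gap, so the figures do not reveal which variance method was used.

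**3. ICC compatible with section 7.1.** Five points at 80% power needs SE = 0.05/2.802 = 0.0178. At an assumed 25% baseline, the unclustered variance is (0.25 x 0.75 + 0.30 x 0.70)/1,935 = 0.000205, so the design effect is 0.0178²/0.000205 = 1.55. With design effect 1 + ICC x [m(1 + CV²) - 1] and m = 4,300/103 = 41.7 or 4,300/155 = 27.7:

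- 103 clinicians: ICC = 0.55/40.7 = 0.014 (CV 0) to 0.55/82.5 = 0.007 (CV 1.0).
- 155 clinicians: ICC = 0.55/26.7 = 0.021 (CV 0) to 0.55/54.5 = 0.010 (CV 1.0).

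Over baselines of 15% to 40% the range is about 0.003 to 0.043.

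**4. Closed-form check, arms only, equal volumes.** Take 10 CDS-MTDM and 46 control clinicians and work in units of the between-clinician-mean variance.

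- True variance: 1/10 + 1/46 = 0.1217, of which CDS-MTDM supplies 0.1/0.1217 = 82%.
- Expected CR1 variance: (103/102) x [0.1 x 0.9 + (1/46)(45/46)] = 0.1124. The SE is therefore too small by a factor sqrt(0.1124/0.1217) = 0.961.
- Satterthwaite df: 0.1217²/[0.1²/9 + (1/46)²/45] = 13.2, not 102.
- CR1 rejects beyond 1.983 x 0.961 = 1.906. On t with 13.2 df the two-sided tail is **7.9%**.

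The same steps with 16 and 70 clinicians give 22.4 df and **6.7%**. For CDS-OS (47 and 46) they give 91 df and 5.2%.

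**5. Simulation with unequal volumes.** Null case, 25% baseline, ICC 0.015, arms-only model, nominal 5%:

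| Clinicians | CR1, t(G-1), at CV 0 / 0.6 / 1.0 |
|---|---|
| 103 | 6.8 / 8.9 / 10.8% |
| 155 | 6.7 / 7.4 / 8.7% |

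CR2 with Satterthwaite df gives 4.8-5.5% over the same settings. A separate simulation at 30% baseline and ICC 0.02-0.05 agrees: CR1 8.0-12.5% (10 v 46 clinicians) and 6.6-9.0% (16 v 70), CR2 4.8-5.7%. In that run CDS-OS (ICC 0.05, CV 0.6) gives 5.6% with CR1 and 5.2% with CR2. With arms plus education main effects, stratified allocation and a wider ICC range (0.01-0.10), CR1 gives 6.3-13.4% (103) and 5.2-10.1% (155), and CR2 gives 3.1-5.6%.

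**6. The retention rule.** If the interaction is kept, the CDS-MTDM coefficient is the effect at the delayed-education baseline. If clinicians split 60/40 as the sites do (3 early, 2 delayed), that cell holds 10.3 x 2/5 = 4.1 CDS-MTDM clinicians. For 4 against 18 controls, df = (1/4 + 1/18)²/[(1/4)²/3 + (1/18)²/17] = 4.4. Following the rule with CR1, and reading H_A2 from that coefficient, gives about 12-21%. Over ICC 0.01-0.10, the joint interaction test itself rejects 12-32% of the time under CR1, against 5.6-8.6% with a CR2 small-sample F. CR2 with the rule left in place still gives 5.7-8.8%, mainly from choosing the model by significance.

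**The case against.** The strongest reply is that the plan fixes the model, the clustering unit, alpha and sidedness, and excludes no corrected estimator. All the inflation is conditional on CR1, which no section names. That stands: this is an omission. A reader might infer that the H_A2 analysis will over-reject, and the documents do not support that.

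The size also depends on inputs the plan does not give. Figures of 10% or more in a fixed model need strongly unequal clinician volumes. With similar volumes and all slots filled, CR1 is close to nominal (5.2-6.9% with education main effects). An ICC of 0.10 exceeds what section 7.1 implies. This limits the size but does not remove the inflation, because step 5 uses an ICC close to the implied range.

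The 12-21% must not be read as the cost of the variance method alone. It comes partly from model selection, and it assumes a joint interaction test and that H_A2 is read at the delayed baseline. Section 7.2.2 fixes the coding but states neither.

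Nor do the documents establish a cell of 4 clinicians. Section 6.1 compares sites on patient load, not on number of clinicians. Late joiners coded as *other* would add nobody to that cell, but no cut-off date is given.

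Finally, one might infer that the 9-point figure is wrong. Step 2 shows that this cannot be told from the text. The figure does already acknowledge lower precision in this arm.

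**Conclusion.** The concern holds as a gap in specification that should be closed. It has two parts.

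- **Variance method.** If section 7.2.3 is implemented with CR1 and t(G-1), type I error for H_A2 in a fixed model is about 7-11% with 103 clinicians and 6.5-9% with 155. This rests on an assumed 25% baseline, ICC 0.015 and volume CV 0-1.0. CR2 with Satterthwaite df restores about 5%. CDS-OS versus control is essentially unaffected.
- **Model choice.** If the section 7.2.2 rule decides the model and H_A2 is read from the CDS-MTDM coefficient, error under CR1 is about 12-21%, under the further assumptions in step 6. A better variance method alone does not fully cure this.

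Confidence is medium: the clinician counts and the silence of the text are firm, but the error rates depend on assumed inputs.

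**What to change.** 1. In section 7.2.3, pre-specify CR2 variance with Satterthwaite degrees of freedom for the CDS contrasts.
2. In section 7.2.2, read H_A2 from one fixed model (arms plus education main effects). Treat the CDS x education interaction as a separate secondary test with the matching small-sample F, so that significance-based retention does not decide the primary contrast.
3. Check whether the 9-point detectable difference used the same variance method, and restate it only if it did not.

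Reporting the realised number of CDS-MTDM clinicians, overall and by education group, would let readers judge the result. A randomization test that respects the strata is an optional sensitivity check.

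The text cost is a few sentences, and standard software suffices. Section 10 says outcomes had not been extracted or examined by arm, beyond a very limited early check of the alerts, so this could still be pre-specified at this version.

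The statistical cost is real. In simulation the CDS-MTDM interval is wider than under CR1 by a median 13 / 18 / 28% with 103 clinicians and 8 / 11 / 17% with 155 (CV 0 / 0.6 / 1.0). Power for 9 points (arms only, ICC 0.01-0.02) falls from 70-87% to 51-79% with 103 and from 76-90% to 64-85% with 155. Part of that loss is only CR1's excess type I error. CR2 can also be somewhat conservative, down to about 3%, if the strata explain most of the between-clinician variance.

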**Other pre-specified effectiveness outcomes:**

- All-cause mortality or emergency visit or hospitalization for heart failure, within 365 days of index visit. This will be assessed as patient death (yes/no), patient with emergency visit with a primary diagnosis of heart failure (yes/no), or admission for inpatient hospitalization with primary diagnosis of heart failure (yes/no).
- Optimal GDMT dosing (at least 50% of target dose) on all classes (with or without ARNI), within 180 days of index visit.
- Increased dosing or initiation for each individual class, within 180 days of index visit.
- Decreased dosing or removal for each individual class, within 180 days of index visit.
- Timing of increases in GDMT over 180 days since index visit.
- Economic outcomes such as (1) return on investment (ROI) and (2) cost effectiveness (CE) of CDS and MTDM interventions compared with standard of care (using modeling approaches specified in the ROI and CE analysis section above).

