#### 7.2.2 Approach for comparisons across intervention arms

*CDS analyses:* We will test whether each outcome differs as a function of each CDS active arm (CDS-OS and CDS-MTDM) relative to no-CDS control. Regressions will include as covariates education arm and interactions between CDS and education. We will retain both terms if the interaction is significant and retain the main effect if only it is significant. The education variable in CDS analyses will be coded as delayed education (baseline), early education, other (for clinicians who were not in the system early enough to be included in an education arm, to avoid either diluting or biasing the education effects).

As an exploratory analysis, we will compare CDS-MTDM against CDS-OS to see which is most effective.

Additionally, covariates will be added to exploratory versions of the final models as sensitivity analyses, to adjust for measured differences across clinicians, such as role, number of patients seen, and baseline rates of prescribing each of the GDMT classes. We have no *a priori* hypotheses about the moderating effects of these covariates.

*Education analyses:* We will test whether each outcome differs as a function of early education relative to delayed education. Regressions will include as covariates CDS arm and interactions between CDS and education. We will retain both terms if the interaction is significant and retain the main effect if only it is significant. Assignment to early versus delayed education is not random; therefore, regression analysis comparing education to no-education controls will adjust for as many relevant covariates as possible, including baseline prescribing rates.

In these analyses, we will exclude clinicians who were not present throughout the data collection period, beginning at assignment to early education. That is, we only intend to include clinicians in early and delayed education arms who theoretically could have been exposed to the education and who then had time to treat patients based on what they learned.

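### The cost-effectiveness rule is valid only for an arm that adds effect, and ICERs against usual care alone can pass CDS-MTDM even when CDS-OS is better value

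*Combined protocol and SAP*

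**What the plan says.** Section 6.8 lists, among the other pre-specified outcomes, "cost effectiveness (CE) of CDS and MTDM interventions compared with standard of care". Section 7.2.3 obtains ICERs from a decision tree with a Markov cohort model and sets the yardstick: "we will define the willingness-to-pay (WTP) threshold as 1 to 3 times the local gross domestic product per capita". The verdict follows from one sentence: "Interventions with an ICER below the threshold will be considered cost-effective".

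Section 7.2.3 also addresses uncertainty: "cost-effectiveness acceptance curves will be generated for all cost-effectiveness measurements", and "The effects of uncertainties from the model parameters will be evaluated by deterministic and stochastic sensitivity analyses". It does not say whether the curves are pairwise or cover all three strategies, or whether they are built on net benefit. The decision sentence does not refer to them.

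Two other places touch on the active arms:

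- Section 7.2.2: "As an exploratory analysis, we will compare CDS-MTDM against CDS-OS to see which is most effective". This concerns effect, not value for money.
- Section 7.2.3, on return on investment, counts savings "attributable to the interventions (CDS-OS + CDS-MTDM) to calculate the corresponding ROI", which pools the arms. Table 3 in section 6.8 lists a return on investment for CDS-MTDM as a maintenance measure, but not against CDS-OS.

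No section mentions dominance, net benefit, or an incremental cost-effectiveness comparison of CDS-MTDM with CDS-OS.

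**The concern.** A ratio of two differences loses information about their signs. A negative ICER can mean cheaper and better, or dearer and worse. A positive one can mean dearer and better, or cheaper and worse. A rule that looks only at whether the ratio is below a positive threshold therefore needs a condition on the sign of the incremental effect, and the plan states none.

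The second issue is more likely to matter in practice. A health system would run one of usual care, CDS-OS or CDS-MTDM. Under Table 1 of section 6.7, CDS-MTDM involves pharmacist contacts repeated every 1 to 2 weeks until therapy is optimized, so what that extra resource buys beyond an order set is the natural economic question. ICERs taken separately against usual care do not answer it. CDS-MTDM can pass although CDS-OS gives more effect for less money, or although its increment over CDS-OS costs more than the threshold allows.

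**Working it through.** **Inputs from the documents.** The rule is ICER < λ, with λ from 1 to 3 times GDP per capita (section 7.2.3). The comparator is standard of care (section 6.8). There are three arms (section 6.1). The documents give no incremental cost, incremental effect, dollar threshold or unit of effect, so there is no figure of the plan's own to reproduce.

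**Assumptions.** Every ΔC and ΔE below is assumed. Costs are in units of GDP per capita and effects in the model's outcome unit, so λ runs from 1 to 3.

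**Step 1: the sign condition.** Let incremental net monetary benefit be NMB = λΔE − ΔC. An arm is worth having if NMB > 0.

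- If ΔE > 0, then ΔC/ΔE < λ is the same statement as NMB > 0. The rule is right.
- If ΔE < 0, multiplying by ΔE reverses the inequality, so ΔC/ΔE < λ is the same statement as NMB < 0. The rule is reversed.

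| Case | ΔC | ΔE | ICER | Rule, λ=1 / 3 | NMB, λ=1 / 3 |
|---|---|---|---|---|---|
| Dearer, better | 0.05 | 0.10 | 0.5 | pass / pass | 0.05 / 0.25 |
| Dearer, better | 0.50 | 0.10 | 5 | fail / fail | −0.40 / −0.20 |
| Cheaper, better | −0.05 | 0.10 | −0.5 | pass / pass | 0.15 / 0.35 |
| Dearer, worse | 0.05 | −0.10 | −0.5 | pass / pass | −0.15 / −0.35 |
| Cheaper, worse | −0.05 | −0.10 | 0.5 | pass / pass | −0.05 / −0.25 |
| Cheaper, worse | −0.20 | −0.10 | 2 | fail / pass | 0.10 / −0.10 |
| Cheaper, worse | −0.50 | −0.10 | 5 | fail / fail | 0.40 / 0.20 |

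The first three rows are decided correctly and the last four wrongly. Rows three and four share an ICER of −0.5 but need opposite decisions.

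**Step 2: three strategies.** CDS-OS is held at (ΔC, ΔE) = (0.02, 0.10) against usual care. Its ICER is 0.02/0.10 = 0.20, and its NMB is 0.10 − 0.02 = 0.08 at λ=1 and 0.30 − 0.02 = 0.28 at λ=3.

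| CDS-MTDM (ΔC, ΔE) | ICER v usual care | CDS-MTDM v CDS-OS | CDS-MTDM NMB, λ=1 / 3 | Better arm |
|---|---|---|---|---|
| (0.09, 0.12) | 0.75, pass | 0.07/0.02 = 3.5 | 0.03 / 0.27 | CDS-OS |
| (0.06, 0.09) | 0.67, pass | dearer and worse | 0.03 / 0.21 | CDS-OS |
| (0.06, 0.15) | 0.40, pass | 0.04/0.05 = 0.8 | 0.09 / 0.39 | CDS-MTDM |

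CDS-MTDM passes in all three rows. It is the better arm only in the third, where picking the lower ICER (0.20 against 0.40) would wrongly favour CDS-OS.

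**Step 3: stochastic analysis, if the literal rule were applied to each draw.** One million independent normal draws were taken, with ΔC of mean 0.05 and SD 0.03, and ΔE of SD 0.05.

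| Mean ΔE | λ | ICER < λ | NMB > 0 |
|---|---|---|---|
| 0 | 1 | 69% | 20% |
| 0 | 3 | 87% | 37% |
| 0.05 | 1 | 65% | 50% |
| 0.05 | 3 | 90% | 74% |

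Even when the arm is better on average, draws with negative ΔE inflate the apparent acceptability.

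**The case against.** The strongest reply is that this is silence, not a wrong rule. Threshold tests are conventionally applied to options that add cost and effect, and dominated options are labelled as such. A competent analyst would probably do that here, and acceptability curves built on net benefit would expose a dominated arm. This has force for the sign problem, which also needs an active arm to be less effective than usual care. It does not remove the problem: the convention is unwritten, and the curves are neither specified nor tied to the verdict.

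Second, the plan does not set out to choose between the active arms on economic grounds. The hypotheses in section 5.2 and the economic outcome in section 6.8 are both against usual care, and being cost-effective against usual care is a legitimate statement about that contrast. A reader might infer that the plan would recommend CDS-MTDM over CDS-OS. The documents do not support that, since they contain no such recommendation step. What stands is that a pairwise pass is easily read as good value when a better-value alternative was tested in the same trial.

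Third, the added contrast will be imprecise. Section 6.1 gives CDS-MTDM 10% of clinicians, and section 7.1 gives it a detectable difference of about 9 percentage points against control, compared with 5 for CDS-OS. Control clinicians may also use pharmacist services (section 6.7). These are reasons to report uncertainty, not to omit the comparison.

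**Conclusion.** The point holds in a limited form. The stated rule is valid only for ΔE > 0. Below that it passes every dominated arm. A reader might infer that it passes every cheaper-but-worse arm too, but it does not: it passes those with an ICER below the threshold (negative net benefit) and rejects those above it (positive net benefit). The more useful finding is the three-strategy one: CDS-MTDM can pass against usual care while dominated by CDS-OS, or while its increment over CDS-OS exceeds the whole threshold range.

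The algebra in step 1 holds for any positive threshold and needs no trial data. All numerical sizes are illustrations from assumed inputs. They show that the error can occur, not how likely it is. The outcome is neither primary nor secondary, and the analyses of GDMT prescribing are untouched. This is a lower-priority change.

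**What to change.** In section 7.2.3, replace the decision sentence with a rule along these lines:

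- Call an active arm cost-effective against standard of care if its expected incremental net monetary benefit is positive, reported at each stated threshold value (1 and 3 times GDP per capita), with the unit of effect named.
- Order usual care, CDS-OS and CDS-MTDM by cost, remove dominated and extendedly dominated strategies, and report ICERs between the neighbours that remain. Always report CDS-MTDM against CDS-OS, as an ICER or as a statement of dominance.
- Identify the strategy with the highest expected net monetary benefit at each threshold value.
- Build one acceptability curve covering all three strategies from net benefit in the stochastic draws.

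Keep the comparisons with standard of care in section 6.8 as they are. The cost is slightly more analysis from the same decision-tree and Markov outputs, with no new data. The increment of CDS-MTDM over CDS-OS will be imprecise, so present it with its uncertainty. Section 10 says outcome data had not been extracted or examined by arm at this version, apart from a very limited alert check, so as of that version the rule could be settled before results were seen.

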**Table 3 Implementation Outcomes**

Variable	Reach	Adoption	Implementation	Maintenance
Focused Education	% of providers completing education	% of clinics receiving education	

• Feedback received from continuing education forms

• Adaptations made from original education plan

	Change in GDMT over time post education vs. control
CDS-OS	

• % of eligible patients where BPA action taken by provider

• % of eligible patients where the BPA SmartSet was opened

	% of eligible clinicians participating in the CDS intervention	Acknowledgement response assessment	Changes in %BPA action taken by providers over time.
CDS-MTDM	

• % of eligible patients where clinician referred to MTDM

• % of eligible patients seen by MTDM

	% of eligible pharmacists participating in the MTDM intervention	Fidelity to HFrEF protocol (e.g. % scheduled within 3 days)	Return on Investment of CDS-MTDM

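### Section 7.2.3 defines one ROI for CDS-OS and CDS-MTDM combined, which as written does not deliver the CDS-MTDM ROI listed in Table 3

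*Combined protocol and SAP*

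**What the plan says.** The ROI method is in the last sentence of Section 7.2.3: "We will also compare the total dollar amount spent on implementing this program against the cost savings, if any", with the savings being those "attributable to the interventions (CDS-OS + CDS-MTDM) to calculate the corresponding ROI". Neither the spend nor the savings is divided by arm. The same section leaves ROI out of the regression models used for most other outcomes: "For all outcomes except timing of GDMT increases and ROI outcomes, ordinary least squares (OLS) regressions will be run".

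Other parts of the document point to results by arm:

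- Table 3 (Section 6.8), CDS-MTDM row, Maintenance column: "Return on Investment of CDS-MTDM".
- Section 6.8, other pre-specified outcomes: ROI and "cost effectiveness (CE) of CDS and MTDM interventions compared with standard of care". For the method it refers to "using modeling approaches specified in the ROI and CE analysis section above". The table of contents lists no such section, and the economic methods appear later, in Section 7.2.3.
- Section 7.2.2: each outcome is tested for each active CDS arm relative to the no-CDS control.

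Section 6.1 allocates clinicians to control, CDS-OS and CDS-MTDM in a "45%/45%/10% proportional distribution".

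**The concern.** An analyst who follows Section 7.2.3 literally produces one ROI and leaves the Table 3 entry empty. An analyst who wants to fill that entry has no method for dividing programme spend between the arms or for attributing savings to one of them. The method would then have to be chosen later, possibly with results in view.

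The two arms differ in how intensively they use pharmacists. Under Section 6.7, the CDS-OS alert leads to an order set. The CDS-MTDM alert leads to an urgent pharmacist referral, followed by repeated pharmacist visits until therapy is optimised. Referral rates are also fed back, and some clinicians have one-to-one discussions about referring. Section 10 adds contact by the lead investigator with low-referring clinicians. One ratio across both arms can hide a gain in one and a loss in the other, and a health system deciding which strategy to keep would not see it.

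**Working it through.** The plan states no ROI, cost or saving, so there is no figure of its own to reproduce. The check covers what the formula can deliver.

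**Inputs from the documents.** Allocation is 45:45:10 (Sections 6.1 and 6.2), with 155 clinicians, of whom 103 are current and 52 hypothetical (Section 6.2), and 4,300 patients (Section 7.1).

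- Clinicians: 155 × 0.45 = 69.75 in CDS-OS and 155 × 0.10 = 15.5 in CDS-MTDM. Among current clinicians only, 103 × 0.10 = 10.3 in CDS-MTDM.
- Patients, if they follow the clinician split: 4,300 × 0.45 = 1,935 and 4,300 × 0.10 = 430.
- Share of the two active arms: 45/55 = 81.8% and 10/55 = 18.2%.

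**Formula.** Let S be savings and C spend, with subscripts OS and M for the two arms.

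Pooled ROI = (S_OS + S_M − C_OS − C_M)/(C_OS + C_M) = (1 − w) × ROI_OS + w × ROI_M, where w = C_M/(C_OS + C_M).

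The weight w is a share of spend, not of clinicians. If patients follow the clinician split, fixed costs are ignored, and r is the per-patient cost ratio CDS-MTDM:CDS-OS, then w = 10r/(45 + 10r). Under equal allocation it would be w = r/(1 + r).

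**Illustration.** Arm ROIs of +1.0 (CDS-OS) and −0.5 (CDS-MTDM) are assumed, as is the range of r. Pooled ROI = 1 − 1.5w.

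| r | w at 45:10 | Pooled ROI at 45:10 | w at 45:45 | Pooled ROI at 45:45 |
|---|---|---|---|---|
| 1 | 10/55 = 0.182 | +0.73 | 0.500 | +0.25 |
| 2 | 20/65 = 0.308 | +0.54 | 0.667 | 0.00 |
| 5 | 50/95 = 0.526 | +0.21 | 0.833 | −0.25 |
| 10 | 100/145 = 0.690 | −0.03 | 0.909 | −0.36 |

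**When allocation alone changes the sign.** The pooled ROI is zero when w = 2/3. At 45:10 this means 10r/(45 + 10r) = 2/3, so r = 9. At 45:45 it means r/(1 + r) = 2/3, so r = 2. With these arm ROIs, the allocation ratio decides the sign only for r between 2 and 9.

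**One pooled value, opposite arm results.** At 45:10 with r = 4.5, w = 45/90 = 0.5.

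- Arm ROIs of +1.0 (CDS-OS) and −0.5 (CDS-MTDM) give 0.5 × 1.0 + 0.5 × (−0.5) = +0.25.
- With the two arms exchanged the result is again +0.25.

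The pooled ratio therefore cannot be worked back to the Table 3 figure.

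**The case against.** The strongest reply is that the bracketed sum in Section 7.2.3 may be shorthand for each of the two interventions. Sections 6.8 and 7.2.2 and Table 3 all lean towards reporting by arm, and Section 7.2.3 exempts ROI from OLS, not from comparison by arm. Arm-level cost and claims data will exist. A programme-level return is also a legitimate budget question, and the wording of the sentence suggests a supplement to the cost-effectiveness analysis. All of this may be so. Even then, the document gives no arm-specific ROI method, so the wording still needs settling.

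A reader might also infer more than the documents support:

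- That the pooled weights are simply 82:18. They are spend shares. In the illustration CDS-MTDM carries 18% only at r = 1, and 69% at r = 10. The 45:10 ratio also counts clinicians, and patient numbers may not follow it.
- That pharmacist cost arises only in CDS-MTDM. Sections 3 and 6.7 allow pharmacist referral in usual care, so the arms differ in degree.
- That the trial cannot yield an ROI by arm. Only the formula as written fails to do so.
- That the cost-effectiveness analysis is pooled too. Section 7.2.3 judges interventions by their ICERs and does not clearly combine the arms.
- That ROI is an improper Maintenance metric in Table 3. The document does not define Maintenance so as to exclude economic sustainability. Tracking referral over time would be an optional addition.

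**Conclusion.** The point holds for ROI: the method in Section 7.2.3 and the entry in Table 3 do not match, and one pooled ratio cannot supply the arm-level figure. This rests on the text and the algebra and needs no cost assumption.

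The practical size is unknown because the documents give no costs or savings. The illustrated range of +0.73 to −0.03 depends on assumed arm ROIs, assumed cost ratios, patients following the clinician split and no fixed costs. It shows that disagreement between the arms can be hidden, and it does not predict that it will be. A change of sign through allocation alone is possible but not general: at r = 1 the pooled figure is positive under both ratios, and at r = 10 it is negative under both.

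ROI is among the other pre-specified outcomes, so the primary and secondary effectiveness results are untouched. The change is still worth making because it is cheap. Section 10 says outcome data had not yet been examined by arm, apart from limited checks of the alerts, so the method could still be fixed in advance at the date of this version.

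**What to change.** Rewrite the ROI sentence in Section 7.2.3 to specify:

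1. ROI for CDS-OS v control and for CDS-MTDM v control, each as (incremental savings − incremental cost)/incremental cost.
2. Arm-specific incremental costs, net of the MTDM use that occurs in usual care.
3. A stated rule for apportioning the shared CDS build cost, and a statement of whether education costs count. Education was assigned by clinic and crossed with all three arms, so its cost is not specific to either active arm.
4. An interval for each ROI from a bootstrap that resamples clinicians within arm.
5. Any pooled programme ROI as secondary, with its spend weights reported.

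Correct the cross-reference in Section 6.8 so that it points to Section 7.2.3.

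The cost is SAP wording and a few more lines of analysis, with no new kind of data. The downside is precision: with roughly 10 to 16 CDS-MTDM clinicians, that ROI will be uncertain and its bootstrap interval only approximate. Reporting the interval shows this uncertainty, which a pooled figure would conceal.
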